Study patients will be randomized into groups 1, 2, or 3 immediately AFTER initial thorough wound cleansing/debriding by the nurse or physician. Randomization will be accomplished using an electronic random number generator (an app).

After a member of the UHWI surgical team performs the initial cleansing/debriding, the control group (1) will have their ulcer dressed as usually done at UHWI. Wounds are dressed with saline-soaked gauze, covered with dry gauze. One wrap of stretch gauze will hold the dressing in place. Patients will clean the wound by vigorously wiping with gauze soaked in homemade normal saline (1 tsp salt/500ml water bottle), center to edges, at each dressing change, unless already very clean. Clean wounds will simply be irrigated with normal saline at each dressing change. Patients experienced with using papaya for debridement of their ulcers may apply it only to the open wound, avoiding contact with the periwound, to remove slough or eschar. If patients observe green exudate, they are permitted to add one teaspoon of vinegar to their bottle of saline. Dressings in group (1) will be changed daily. The dressings will be soaked off if they become adherent.

After initial cleansing/debriding, patients in the improvised dressing group (2) will then have a thin layer zinc oxide paste applied to the dried periwound, carefully avoiding the open wound.⁹⁷ A piece of a clean new plastic bag (food-grade World Star 1 mil LD bags, or the equivalent, purchased from the Papine Market across John Golding Road from the University of the West Indies), cut slightly larger than the ulcer will be gently conformed to the moist wound contours and sealed onto the zinc oxide paste. The bag will be fenestrated with a small slit using a number 11 scalpel or clean scissors prior to placing it on the ulcer in order to allow excess fluid to escape. The edges of the slit will be approximated. Clean gauze will be placed lightly over the slit to capture escaping fluid. One wrap of stretch gauze will hold the dressing in place. Patients will be instructed to change the dressings daily, irrigating with normal saline at each dressing change.⁶

After initial cleansing/debriding, the advanced dressing group (3) will have a cut piece of a 4"x24" standard (pink) PMD roll large enough to extend at least 0.5 cm beyond all open and closed (inflamed or damaged) wound edges applied as per the Instructions for Use (the periwound is blotted dry, but the wound bed remains moist from the final saline rinse). One wrap of stretch gauze will hold the PMD dressing in place. The approximate open wound edges will be marked on the dressing backing. As per the manufacturer's instructions for use, patients will change the dressings when saturation reaches any of the wound edges, as indicated by a change in color on the backing of the dressing, visible through the stretch gauze. Routine rinsing will not be performed; the wounds will be rinsed at dressing changes only if visible loose debris is present.

All study patients will receive education about their illness and pain medication prescriptions per usual protocol. Patients are advised to use a compression wrap whenever their foot is dependent, as often as they are able to tolerate it. They will each be given a zipper-bag to contain and keep their wound management supplies clean.

Patients will be required to come to the UHWI surgical clinic dressing area in person weekly during the initial 4 weeks of study enrollment so that wound photos can be taken and the data for the ten dependent variables that are to be assessed weekly can be obtained. If their SCLU is clean without evidence of complications, patients/families who demonstrate the ability to take adequate pictures of their study SCLU with their mobile devices may instead send photos of their wound and their data collection sheets to the research team via end-to-end encrypted text messaging system (WhatsApp). All patients must agree to come to UHWI at least once per month to avoid being withdrawn from the study. Appointment times will include evenings and Saturdays to accommodate the schedules of students and employed patients.

Weekly, de-identified photographs will be sent by the Principal Investigator to be viewed by two blinded wound experts ([name] and [name]) off site. If the blinded experts, or anyone else involved in the study, expresses concern that a patient is exhibiting signs of possible infection, maceration that is delaying healing, or wound deterioration, a physician at UHWI or the SCU who is not otherwise involved in the study will be asked to evaluate that patient. The patient's dressings will be removed prior to this evaluation so that their treatment group will not be revealed to the physician (the evaluation by the physician is thus blinded to treatment group). If the physician determines that the patient's condition has not improved with the prescribed treatments (e.g., antibiotics), the patient will be withdrawn from the study. Any

patient who transitions out of the group to which they were randomized for any reason will receive usual treatment for their ulcer for the remainder of their 12 week study period.

When the treatment personnel at UHWI or the blinded remote observers state that the patient's wound appears to be closed, a physician at UHWI or the SCU who is not otherwise involved in the study will be asked to evaluate that patient. The patient's dressings will be removed prior to this evaluation so that their treatment group will not be revealed to the physician. Wound closure is defined as 100% epithelialized with no discernible scab or exudate production (a paper napkin blotting the area remains dry). Patients will be reassessed two weeks later to verify that the wound was truly closed and did not immediately recur.

Patients who are diagnosed with wound closure or have completed the 12 week study period will be taken aside privately and asked to rate the acceptability of their treatment using a 5 point Likert Scale. A family decision-maker will also be privately asked to rate the acceptability of the treatment. One of the research team members will enter this basic acceptability data for the patient and the family on the patient's Data Collection Tool. At that point, the patient will graduate from the study. However, patients and families will be instructed to return to UHWI for follow-up if a complication or recurrence develops. Any delayed complications (e.g., recurrence within 3 months) will be recorded on the patient's Data Collection Tool by the nurse or physician to whom the patient reports it.

As a token of appreciation from the research team and an incentive for patients to return for their study clinic visits, each participant will be presented with a 500JM phone card at the end of each of the three 4-week study periods.

All wound management supplies for all three groups will be donated. Shipping and handling fees will be paid by the Principal Investigator with funds from a Wound Healing Foundation grant. Tallies of supplies used at dressing changes will be priced using the cost of medical supplies purchased by the SCU to determine the estimated cost of the treatment supplies for each patient. The PMD rolls will be valued at \$26.99US.⁹⁸

The Principal Investigator will de-identify the data and compile it from the patient Data Collection Tools onto an Excel spreadsheet. This spreadsheet and the de-identified wound photographs will be backed up onto the Principal Investigator's second password protected hard drive via a secure internet connection at least weekly. Two encrypted USB drives containing the data, including wound photographs, will be updated weekly on an alternating schedule and stored in a securely locked file in [name] office in UWI Department of Surgery.

i. Statistical analysis

A consultant, [name], PhD, Senior Biostatistician at The University of Texas Medical Branch in Galveston, will undertake the analysis.

When all of the patients have completed the study, the remainder of the data from the deidentified Data Collection Tools will be transcribed into an Excel spreadsheet by the Principal Investigator. The data will then be evaluated by the biostatistician using the most recent version of SPSS. Groups will be compared with respect to each of the 14 dependent variables, taking into account any confounding from the 11 independent variables. Results will be reported using descriptive statistics (means, modes, medians, frequencies), student's t test, and ANOVA with 95% CIs, using intent-to-treat.¹³ If the improvised dressing does not attain statistical superiority to usual practice, 80% CIs will be calculated with drop-outs removed from the analyses to evaluate noninferiority.^{13, Appendix: From Oczkowski SJW} Complications will be evaluated both individually and collectively by collapsing the pertinent columns.

Research questions (1) and (2) will be addressed by using analyses of covariance (ANCOVA) to determine if patients in the improvised dressing group (Group 2) had superior results (95% CI's will fall within *f*, the superiority margins) from usual practice (Group 1) or advanced dressings (Group 3), or, if this is not demonstrated, failed to vary significantly (80% CI's will fall within *f*, the inferiority margins) from usual practice (group 1) or advanced dressings (group 3) with respect to each of the dependent variables, controlling for relevant patient characteristics (the independent variables).

Research question (3) will be addressed with descriptive statistics across Likert items regarding endorsement of and concerns with use of the improvised dressing clinically or in future studies. Qualitative comments will be summarized across providers into content themes. Any differences between nurses, patients, family members, and physicians will also be explored and noted.

All health care providers at UHWI participating in the study will be surveyed to explore their concerns as well as their opinions about each dressing choice, using both qualitative open-ended and a quantitative question on a Likert scale. Results will then be shared with the participating clinical staff to provide them with the evidence concerning each of the three dressing protocols.

j. Data handling and record keeping

All study data will be transferred from written documents to the Principal Investigator's password protected electronic devices, de-identified, and then transmitted over secure internet connections to the backup hard drive in the USA. The paper study documentation and the two encrypted USB drives containing the raw data will be stored in a securely locked file in in [name] office in UWI Department of Surgery for a period of at least two years after the study has been published, after which they may be destroyed.

When all of the patients have completed the study, members of the UHWI research team will proofread the Excel spreadsheet with the de-identified data for transcription errors. This data will then be evaluated by the biostatistician using the most recent version of SPSS.

4. Ethical Considerations

This study will be approved by the Ethics Review Committee (ERC) at UWI and the Jamaican Ministry of Health (MOH) prior to its implementation. It will be listed on clinicaltrials.gov prior to the recruitment of the first study patient.

The patients, and available adult relatives of all eligible patients ages 13 to 18, will have the study explained to them by a member of the research team. Questions will be addressed

thoroughly. Patients and families will be assured that if they choose not to participate in the study, their SCLUs will be treated with usual practice. The patient, and in the case of a participant under the age of 18, a parent or guardian, must sign the consent for the patient to be enrolled in the study. Students will be accommodated after school or on a Saturday.

Time required to complete the weekly assessments for the study will create a burden for the study participants (approximately 30 minutes per week, total, and half a day once a month when patients come to UHWI in person for evaluation). However, dressing changes for the two comparator dressings are expected to be less painful and less time consuming than usual practice. In addition, all participants will be given study dressings and their wound care will be provided free of charge. Further, all study participants will be give a zipper bag of the dressing materials of their choice (gauze, plastic bags, or PolyMem; plus a roll of tape and a roll of stretch gauze) at the conclusion of the study.

This study is a collaborative project between the UHWI surgical team and the [name] research team. In addition to her role as an independent researcher for tropical developing countries, as is stated in Ethics Checklist, [name] is an employee of Ferris Mfg. Corp., makers of PolyMem Dressings. This research study falls under her role as Charity Liaison for this company. The study has been designed with a high degree of rigor to help ensure that the results will not be biased as a result of this relationship.

The researchers anticipate that what is learned from this study can directly benefit the urbandwelling Jamaican participants. In addition, many participants will benefit indirectly from the knowledge that their participation in the study can contribute to improving the lives of wound patients living in the rural areas.

SCLUs are often disabling, scarring, and exquisitely painful. The research literature suggests that both the improvised dressing and the advanced dressing can decrease pain. The advanced dressing has also been shown to decrease scarring. However, children ages 13 - 18 are an especially vulnerable population. They are included in the study because this is the peak age group for SCLU formation, and therefore they are the most likely to benefit if the results can be generalized to them.¹⁵

5. Limitations

Blinding is a challenge inherent to studies of wounds. Although the the healthcare professionals who will monitor and verify wound closure and complications (outcomes) will be blinded, it is not possible to blind the participants or the research team members, because they will provide the wound management in this study.

Despite the incentives to remain in the study (phone cards monthly and wound management supplies at the conclusion of the study), it is possible that there will be a substantial dropout rate, because it is easy for patients with SCLUs to become discouraged, and they may feel that they have derived the major benefits of joining the study after the first few weeks.

All of the published studies of improvised dressings describe wound care performed by health professionals based in urban hospitals or long term care facilities. Although this study will be conducted in a tropical outpatient setting, it too is being conducted by health care professionals in an urban area. Also, Jamaica is significantly more developed than many of the countries for whom the improvised dressing educational program may be beneficial. Therefore, this study may not uniformly generalize to rural areas of tropical developing countries, where health professionals are absent.

6. Acknowledgments:

The researchers would like to thank all participants in the study.

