A Test of the Safety, Effectiveness, and Acceptability of an Improvised Dressing for Sickle Cell Leg Ulcers in a Tropical Climate

NCT04479618

As of June 3, 2021

IV. Project Proposal

1. Introduction:

a. Review of Literature

Sickle Cell Leg Ulcers:

One in 300 Jamaicans have the most serious form of sickle cell disease (HgbSS), and of these, between 30% and 70% will suffer from sickle cell leg ulcers (SCLUs).^{1-4,10} Although leg ulcers can affect any age group, by far the majority of sufferers develop their first SCLUs when they are between the ages of 10 and 19.^{2,18}

The SCLUs occur in a younger population, so comorbid conditions such as hypertension, diabetes, peripheral arterial or venous disease, and congestive heart failure are uncommon.¹⁶

SCLUs are found most often along the malleoli, followed by the shins.^{8,10} SCLUs heal 16 times slower than notoriously difficult to heal venous leg ulcers, and in some patients, they never heal, even with decades of expert wound management.^{3,5–7,16} SCLUs often enlarge during the first four weeks of management, and when they do close, they have a higher incidence of recurrence.^{8,16}

SCLUs have an even more negative impact on patient physical quality of life when compared to a myocardial infarction, kidney dialysis, or diabetic foot ulcer.¹⁷ Pain is unrelated to SCLU size and required high doses of opioid, which does not always provide adequate control.^{3,9,11,15,18,19} Because SCLUs often compromise education and employment opportunities, improving wound care for this population benefits the entire community in which they live.^{9–11}

Singh and Minniti, and Clare, Serjeant, et al., defined chronic SCLUs as those with greater than one month duration.^{3,20} Factors affecting the formation and healing of SCLUs or progression to a chronic condition remains elusive.²¹ The correlation with poverty, high serum lactate dehydrogenase, and lower leg venous system damage with SCLUs has been reported.^{3,7,10,18,20} Higher base line hemoglobin levels offer a protection against SCLUs.³ Slough, which is a byproduct of inflammation, is a hallmark of these chronic wounds.^{4,22} Compression therapy and bedrest improve healing of SCLUs, just as they improve the healing of venous ulcers not associated with sickle cell disease.^{3,15,18}

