Although there are as yet no specific proven topical treatments that improve SCLU healing, based upon one small study of SCLUs and results from venous leg ulcer studies, experts recommend moist wound dressings for SCLUs.^{18,69} Moist dressings have been trialed at the Sickle Cell Unit in Mona, Jamaica, without proven benefit over usual practice. Honey, Unna boots, plastic wrap used circumferentially (a completely different technique from the one proposed here), and hydrocolloid dressings failed to produce superior results and/or were not accepted by patients, largely due to the warm climate. Because no moist wound healing method has been found safe, effective, and acceptable to the SCLU patients thus far, saline soaked gauze is the usual practice throughout Jamaica (as is the case throughout the world). However, comparing the improvised dressing only to saline-soaked gauze would virtually assure the impending obsolescence of the study results, because saline-soaked gauze does not stay moist and has been considered to be substandard care among wound management experts for over a decade.^{18,32–34,70,71} Therefore, the only advanced moist wound dressing with a strong record of success when used in the tropics will be included as a positive control in this study.⁷²

Polymeric membrane dressings (PMDs, PolyMem[®], Ferris Mfg. Corp., Ft Worth, TX, USA) are unquestionably the advanced moist wound dressings with the most evidence to support their use in rural areas of tropical developing countries.^{72–77} PMDs do not melt, break apart, or become adherent in a warm environment, and they are well tolerated in the tropics.^{72,78,79} The continuous cleansing system that is an integral function of PMDs has been demonstrated to mitigate the problem of increased infections in the tropics.^{72,79} PMDs also control inflammation and decrease

pain, two key influencers of healing in venous ulcers which may translate to sickle cell ulcers.^{14,72,80} When used on venous leg ulcers, with or without compression, PMDs increased wound closure rates, sped healing, and decreased pain.^{14,78} In addition, PMDs are among the very few advanced wound dressings mentioned favorably in the sickle cell literature.^{7,9}

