Real world applicability of a study is enhanced if exclusion criteria are kept to a minimum. However, clear confounds should be avoided. Miller, et al., found that in young surgical patients, diabetes, cancer, kidney disease, hypertension, and abnormal BMI all significantly increased the chances of wound complications, while COPD, smoking, age, and HIV status did not.⁸² Yang, et al., found that smoking, hypertension, age, diabetes, and obesity did not delay VLU healing, and that males were more likely to have delayed VLU healing.⁸³ In contrast, Lane, et al., found that smoking dramatically reduced pressure injury healing, and McDaniel and Browning found that smoking negatively impacts chronic wound healing by impairing neutrophil function and fibroblast activity; decreasing both white and red blood cell production; increasing carbon monoxide, hydrogen cyanide, and other toxic compounds; causing tissue hypoxia; and causing the release of catecholamines.^{84,85} Smoking cessation programs led to improved wound healing.^{84,85} Parker, et al., found that delayed venous ulcer healing was correlated with living alone, ulcer duration > 24 weeks, and age > 70 years.⁸⁶ A review of studies of venous leg ulcer management demonstrated that 12 weeks were sufficient to determine if a treatment was effective or not.⁸⁷

2. Research Questions/Aim:

This study's primary purpose is to determine if an *improvised dressing*, made from inexpensive materials available for purchase in rural as well as urban settings, is a safe and effective, culturally and medically acceptable choice for managing sickle cell leg ulcers in a tropical climate. Three research questions will be addressed:

(1) Is the *improvised dressing*, consisting of a cut-to-fit new plastic bag sealed at the periwound with zinc oxide paste, safe and effective (see definitions, below) when compared with usual practice (saline-soaked gauze) and when compared with an advanced wound dressing (PMD), on sickle cell leg ulcers (SCLUs) in Jamaica?

(2) Does use of the *improvised dressing*, when compared with usual practice, improve the quality of life of patients (decrease pain, increase ability to engage in desirable activities, decrease wound-related materials costs, decrease time required to perform dressing changes, improve Wound QoL scores, and improve ASCQ-Me pencil-and-paper interview scores) with SCLUs in Jamaica?

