(3) Is the *improvised dressing* culturally acceptable to health care providers, patients, and families for managing SCLUs in Jamaica?

The expected study outcome is improvised dressing superior effectiveness and quality of life, when compared with usual practice, without increased safety and acceptability issues.^{13,59,60,62} The improvised dressing is likely to be the least expensive choice, with the added benefit of being available as first aid treatment throughout Jamaica. The advanced dressing is likely to be more expensive with respect to materials costs, although fewer dressing changes are anticipated and pain medication expenses are likely to be reduced. Based upon the review of the literature, no serious infections or other safety issues are anticipated for any group. However, to ensure that complications are not overlooked, in addition to the onsite researchers' vigilance, weekly wound photos will be assessed for complications (signs of infection, wound deterioration, or clinically relevant maceration) by two off-site blinded wound experts, Drs. [name] and [name].

Definitions:

Sickle cell leg ulcer – a wound in a HbSS or HbS β^0 positive patient, open greater than one month,⁷ below the level of the knee excluding the plantar surface of the foot.

Closed wound -100% epithelialized with no discernible scab or exudate production (paper napkin remains dry when lightly pressed against area, and no recurrence in the subsequent two weeks)

Safe – infection and other complications (healing-impairing maceration, keloid, and contracture rates) not statistically significantly higher than usual practice, with no major adverse events attributable to the method

Effective – ulcer closure rates or ulcer surface area reduction rates not statistically significantly lower than usual practice

Acceptable – average acceptability scores of 4 or higher on a 1-5 scale

3. Methods and Materials

a. Study design

This study will be a targeted-blinded (the off-site wound experts and the local physicians verifying wound closure and/or complications will be blinded to the randomization group), randomized controlled trial with three arms: (1) usual practice (negative control), (2) the improvised dressing, and (3) the advanced dressing (positive control). The expected outcome is improvised and advanced dressing superiority.

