Although non-inferiority is an acceptable outcome for the improvised dressing, the review of the literature supports the expectation that it will outperform usual practice. This superiority study design eliminate the motive for the blinded evaluators to minimize differences between groups, biasing the results.¹³ If superiority is attained, the results will be evaluated with intent to treat (ITT) analysis.

If superiority is not demonstrated, the data for the improvised dressing and usual practice dressing will be re-evaluated to assess for noninferiority.¹³ Contrary to superiority trials where use of intention-to-treat is employed to protect against type 1 error, the appropriate approach for noninferiority trials is to use a per-protocol approach,¹³ which, at worst, would exaggerate the differences between treatment groups, thereby yielding a more conservative estimate in the setting of a noninferiority trial.¹³ Thus, only those patients completing treatment in the group to which they were randomized will be retained for any non-inferiority analyses (see appendix for further details).

b. Study population

Individuals diagnosed with sickle cell disease who have a SCLU and reside in the parishes of St. Catherine, St. Andrew, or Kingston parishes of Jamaica and respond to advertisements, recruitment phone calls, or flyers posted at the Sickle Cell Unit (SCU) clinic and UHWI prior to and during the enrollment period will be invited to participate in the study. Members of the UHWI surgical team will call all patients identified by the SCU as having had a SCLU within the past two years to invite them to participate in the study. Jamaican residents who otherwise qualify but who live outside the study area will be included only if they agree to provide their own transportation and faithfully attend all clinic visits.

c. Sample

Study participants must have HbSS or HbS β^0 sickle cell disease, be between the ages of 13 and 70, and have a chronic SCLU, defined as a wound in a patient with sickle cell disease that has been open for at least one month and is below the knee, excluding the plantar surface of the foot. All SCLUs on a single patient will be dressed with the same dressing protocol. The largest ulcer at initial presentation is the study SCLU. If two or more SCLUs in close proximity join into

an enlarged ulcer during the first four weeks of the study, the sum of the initial areas will be considered the initial wound size for calculation purposes.

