- Based upon previous studies and the Central Limit Theorem, an estimated 90 participants (~30 per group) may be required for the differences between groups to reach statistical significance.^{12,23,88,89,96} Up to 120 patients will be recruited to allow for a 25% dropout rate. Based upon the literature review, pain, costs, wound size, and quality of life are expected to be significantly improved using the improvised dressings. However, because SCLUs are, historically, very slow to heal and often enlarge, complete wound closure is not an expected outcome for all patients.

g. Procedures for recruitment and consent

The study will be advertised using free community information channels such as church bulletins and radio outlets. Social media sites such as the CAIHR Facebook page will also be employed. Qualifying patients in the SCU database from up to two years prior to the study initiation will be called by the UHWI surgical team, alerting them to the dates for registering to participate. Flyers will be posted at the SCU in advance. Consent will be obtained by a member of the research team while the potential participant is waiting to be seen for wound care.

h. Data collection

The site for this study is the surgical clinic dressing area at the University Hospital of the West Indies (UHWI), Mona, Jamaica. The adjacent Sickle Cell Unit (SCU) will refer any SCLU patients to UHWI during the study period. UHWI is consistently well staffed with competent Jamaican health professionals. The UHWI surgical team will lead the study. Relatively few Jamaicans live or work in air-conditioned environments, ^[data in appendices] allowing the results from this out-patient population to translate to less developed tropical countries.

To ensure consistency, members of the research team will practice until they can demonstrate competency with all three dressing change procedures and with explaining the study forms prior to study patient recruitment.

Enrollment in the study will begin within two weeks of the day the Principal Investigator arrives at the Mona campus and will close 60 days later, or when a maximum of 120 patients have enrolled. All sickle cell positive patients presenting to UHWI with lower leg ulcers during the enrollment period will be screened for eligibility to enter the study. Each patient's data will be recorded for a total of 12 weeks, or until their SCLU has been closed for 2 weeks, whichever comes first.

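### The definition of Effective asks only for no significant shortfall against a negative control, and its closure route rests on a 12-week window borrowed from venous ulcers

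*Combined protocol and SAP*

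**What the plan says.** **Success rule.** The Definitions in section 2 make a dressing *Effective* when its closure rate or its area reduction rate shows no statistically significant shortfall against usual practice. No margin is attached. Section 3a lists the arms as "1) usual practice (negative control), (2) the improvised dressing, and (3) the advanced dressing (positive control". It tests superiority first and then adds: "Although non-inferiority is an acceptable outcome for the improvised dressing". Section 3i assesses that fallback differently, with an 80% confidence interval set against a margin *f* and drop-outs removed.

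**Reference arm.** Section 1b says saline-soaked gauze "has been considered to be substandard care among wound management experts for over a decade" and adds the polymeric membrane dressing (PMD) as a positive control for that reason.

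**Follow-up.** Section 3h fixes it: each patient's "data will be recorded for a total of 12 weeks, or until their SCLU has been closed for 2 weeks". The only reason offered is in section 1b, which reports from a review of venous ulcer studies that "12 weeks were sufficient to determine if a treatment was effective or not". Section 1a says "SCLUs heal 16 times slower than notoriously difficult to heal venous leg ulcers" and "SCLUs often enlarge during the first four weeks of management". The plan does not reconcile these statements.

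**Outcome.** Section 3c names area reduction as the outcome for research question 1. Section 3f says closure is not expected in every patient. The *Effective* definition still offers closure as an alternative.

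**The concern.** There are two separate weaknesses.

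First, a non-significant difference is not evidence of similarity, and similarity to a negative control is not evidence of an effect. Under the definition, a dressing that adds nothing to usual practice will nearly always be reported as effective, and a moderately worse one will be reported so about half the time. The trial's stated purpose is to validate and promote the improvised dressing, so that label is the main product of the study.

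Second, the adequacy of 12 weeks is carried over from a disease that the plan itself describes as healing far faster. This matters most for closure. If few ulcers close in any arm, comparing closure rates cannot reveal harm, yet under the definition that comparison could by itself earn the label.

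**Working it through.** **Plan's own figure.** 30 × 3 = 90 evaluable patients, and 90 / (1 − 0.25) = 120 recruited, as section 3f states. The 30 per arm cannot be re-derived, because no effect size, SD or power is given.

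**Area route.** Inputs: n = 30 per arm (section 3c); 95% intervals (section 3i), read as a two-sided 0.05 test; true shortfall d in SD units (assumed). The dressing passes unless it is significantly lower:

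P(pass) = P(T > −t₀.₉₇₅,₅₈), where T is noncentral t with 58 df and noncentrality −d√(n/2) = −d√15.

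| True shortfall d | P(called effective), n = 30 |
|---|---|
| 0 (identical) | 97.5% |
| 0.3 SD | 79% |
| 0.5 SD | 52% |
| 0.8 SD | 14% |

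Hand check at d = 0.5: the critical value is about 2.00 and 0.5 × √15 = 1.94, so P ≈ Φ(2.00 − 1.94) = Φ(0.06) ≈ 0.52. With 40 per arm (all 120 analysed), d = 0.5 passes 40% of the time. The d = 0 row is 1 − 0.05/2 and contains neither n nor follow-up. It would be the same at 12 × 16 = 192 weeks.

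**Closure route.** Assumptions: 12-week venous closure v of 30%, 50% or 70% (the documents give no rate), and 16 times slower read as a hazard ratio of 1/16. SCLU closure is then q = 1 − (1 − v)^(1/16).

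| v | q | Expected closures, 30q | P(pass) if the dressing never closes an ulcer | Same, if usual practice closed at rate v |
|---|---|---|---|---|
| 30% | 2.2% | 0.7 | 99.996% | 7.7% |
| 50% | 4.2% | 1.3 | 99.9% | 0.02% |
| 70% | 7.2% | 2.2 | 98.1% | <0.001% |

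The pass probabilities use a two-sided Fisher test. Against 0/30, usual practice needs at least 6/30 closures for significance (6 vs 0: p = 0.024; 5 vs 0: p = 0.052). Simple division, v/16, gives 1.9% to 4.4% closure and the same conclusion.

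**Margin-based fallback.** This is a different test from the definition. If the true difference is zero, the chance that the 80% interval clears a margin m (in SD units) is about Φ(m/√(2/30) − 1.28). For assumed margins of 0.5, 0.3 and 0.2 SD this gives 74%, 45% and 31%. The 97.5% therefore belongs to the section 2 definition, not to the rule in section 3i.

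**The case against.** The strongest reply is that the plan tests superiority first, expects it, and openly defines effective relative to usual practice. Section 1b seeks a cheaper and less painful option, so being no worse than current care is a legitimate aim. That stands, and the fix keeps that claim available. It does not justify the word effective, or the use of non-significance to earn it.

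A reader might infer that the short follow-up is what lets an inert dressing pass. The documents do not support this for area, the outcome named for question 1, because the pass rate is the same at any duration.

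A reader might also infer that all arms will show little change by week 12, or that usual practice has no effect to preserve. No healing rate is given for this arm. It includes initial debridement and regular cleansing (section 3h), and all arms receive advice on compression, which section 1a says improves SCLU healing. Early enlargement also shows that area can move within the window. Nor is 12 weeks shown to be uninformative for area: section 1a describes plastic-wrap trials in slow-healing pressure ulcers that reached significance by weeks 8 and 12, though the plan does not cite them as its reason for 12 weeks.

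The PMD arm is not idle. Section 3i compares it with the improvised dressing in both the superiority and the fallback analyses. What is missing is any link between the PMD versus usual practice contrast and the conclusion. A hard requirement that PMD win would go too far, since section 1b says no topical treatment is proven in SCLUs.

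The appendix on noninferiority is not in the text available, so no criticism is made here of the margin's value.

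**Conclusion.** The point holds as two linked but distinct weaknesses, and it should be fixed.

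- **Definition.** A dressing identical to usual practice qualifies on area 97.5% of the time, and one 0.5 SD worse about 52% of the time. This rests on 30 per arm, a two-sided 0.05 test and an assumed SD-scale shortfall. It is independent of follow-up, except that duration may alter how large a true shortfall becomes.
- **Horizon.** The venous-ulcer justification is not reconciled with the plan's own 16-fold statement. On the assumed venous closure rates and the hazard-ratio reading, about 2.2-7.2% of SCLUs close by week 12. Even a dressing that closes nothing then passes the closure route at least 98% of the time. If the word *or* in the definition means that either route suffices, closure alone confers the label.

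The documents do not establish that 12 weeks is too short for area, or that usual practice is inert.

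**What to change.** 1. **Section 2, Definitions.** Reserve *effective* for superiority over usual practice on ulcer area. Remove closure as an alternative route and report it descriptively.
2. **Sections 3a and 3i.** If superiority is not shown but the noninferiority rule of section 3i is met, conclude only that the dressing was no worse than usual practice over 12 weeks, and say that effectiveness beyond usual practice was not shown. Report the PMD versus usual practice difference with its confidence interval alongside, as context on assay sensitivity. Do not treat a failure of PMD alone as proof that the trial lacked sensitivity.
3. **Section 1b.** State that the venous-ulcer evidence does not carry over directly, and that 12 weeks is meant to support a conclusion on area change.

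The cost is one definition, one conclusion rule and one rationale sentence. No extra data are needed, because section 3i already compares all groups. The downside is that a noninferior-only result supports a weaker claim than the present wording allows.
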